1.1 Title

An exploratory randomized controlled study to evaluate the effect of basic skin care products on the structural strength of the dermo-epidermal junction

1.2 Trial registration

Will be done at clinicaltrials.gov after positive approval by the Ethics Committee.

1.3 Protocol version

Version 1, February 28, 2018

1.4 Funding

This investigator-initiated study (IIS) is conducted and funded by the Clinical Research Center for Hair and Skin Science, Department of Dermatology and Allergy, Charité – Universitätsmedizin Berlin.

2.1 Background and Rationale

The world population is growing, and the life expectancy has risen continuously in developed and developing countries. One consequence is an increase of age associated disabilities and diseases (Kuhlmey A, 2008). The process of aging involves numerous structural and functional changes also affecting the skin. The skin is often considered as the largest organ of the human body and it fulfills a variety of protective and regulatory functions. Compared to other organs, the skin is constantly exposed to harmful environmental influences. Besides intrinsic factors these external factors may accelerate skin aging. Due to its ageing-related loss of functional capacity the skin becomes susceptible to develop adverse skin conditions and dermatological diseases (e.g. skin dryness, fungal infections) (Chang *et al.*, 2013, Kottner *et al.*, 2015). Especially old aged, care depended, and severely ill individuals are at high risk for developing severe skin injuries and wounds (e.g. decubitus, skin tears) with high social and economic impact. Empirical evidence indicates that the reduced adhesion of the dermal-epidermal junction is a major pathophysiological predictor for these types of injuries.

In the field of skin research various non-invasive *in vivo* measurements are established, e.g. measurement of transepidermal water loss or stratum corneum hydration (du Plessis *et al.*, 2013). However, most of these measurements are indirect and these parameters only quantify the properties of the most superficial epidermal layers. The suction blister model is an artificial and controlled technique for dermal-epidermal separation along the dermo-epidermal junction (DEJ) (Unna, 1878, Kiistala and Mustakallio, 1964, Kiistala and Mustakallio, 1967). Empirical evidence suggests that the time of the dermal-epidermal separation (blistering time) is a measure of the dermo-epidermal adhesion. It has been proposed that the blistering time might be a clinically relevant parameter reflecting the mechanical integrity/stability of the dermo-epidermal junction (Hatje *et al.*, 2015).

Cosmetics and basic skin care products are widely used during the entire lifespan. People spent substantial amounts of money for that. In addition, topical skin care products are explicitly recommended to mitigate the increased risk in vulnerable populations, to protect the skin and to keep it intact. For instance, clinical practice guidelines recommend the use of topical skin care products to reduce the risk for pressure ulcer and skin tear development. However, the underlying working mechanisms of most basic skin care products are poorly understood. It is known that topically applied skin care products exhibit physical and chemical effects on and in the uppermost skin layers (e.g. the stratum corneum). Despite a few well known active ingredients (e.g. retinoids, vitamin C) exhibiting effects in the dermis, a particular skin protective effect of the vast majority of daily basic skin care applications on these deeper skin layers is unknown. Interestingly, results of a clinical trial including aged care residents from Australia suggest a protective effect of basic topical

skin care application for preventing skin tears, but the underlying mechanism remains unclear (Carville *et al.*, 2014).

2.2 Objectives

The main aim of this study is to investigate in a suction blister model, whether the use of a basic skin care formulation increases the mechanical integrity/adhesion of the dermo-epidermal junction.

2.3 Trial design

Exploratory randomized controlled study with a split body design on two investigational areas of the anterior side of both forearms.

3 Methods: Participants, interventions, and outcomes

3.1 Study setting

The study will be conducted at the Clinical Research Center for Hair and Skin Science (CRC), Department of Dermatology and Allergy, Charité – Universitätsmedizin Berlin. Screening, inclusion and all study visits including the induction of the suction blisters and the measurement procedures will be conducted at the CRC. Daily application of the skin care product will be conducted at home by the subjects.

3.2 Eligibility criteria

Inclusion criteria

- Healthy volunteers and/or with stable chronic condition (e.g. controlled hypertension)
- Female,
- 65 to 85 years,
- Caucasian,
- Phototype I to III according to the Fitzpatrick classification,
- Body Mass Index between 20 and 28 kg/m²,
- Non-smoker of at least one year,
- Absence of skin diseases or scars in the skin area of interest,
- Absence of tattoos in the skin area of interest,
- Able to give written informed consent,
- Willing and able to fulfill the study requirements

Exclusion criteria

- Known or suspected defect of healing,
- Diabetes mellitus
- Any acute or chronic pathology that may interfere with the trial conduct, from investigator point of view,
- Acute or chronic wounds in the skin area of interest,
- Any skin affection which may interfere with the trial assessment, like urticaria,, psoriasis or scar on investigational areas,
- Medical history of skin cancer,
- History or establishment of diabetes or pre-diabetes,
- Any hyper-sensibility to one of the compounds of the investigational product,
- Any regular treatment which may affect the blood coagulation and hemostasis (anticoagulant medications, NSAID, etc.) before the suction blister induction (Visit 3 and Visit 5), one NSAID to treat headache within four days is allowed
- Any physical treatment (like laser or surgery) on the arms within the last 6 months,
- Use of topical or systemic treatment on the investigational areas within the past 4
 weeks (topical hyaluronan, anti-inflammatory drugs, corticoids, retinoids, vitamin C,
 etc.) that would interfere with assessment and/or investigational treatments,
- Allergy to band-aid or to metals (such as nickel),
- UV sessions or strong sun exposure of the arms during the study period,
- Subject who cannot be contacted easily in case of necessity,
- Current participation in any other clinical study

3.3 Interventions

After giving informed consent and checking the in- and exclusion criteria, baseline skin measurements will be conducted (Table 3). After that one arm will be randomly selected. Subjects are instructed to apply on the selected forearm petrolatum (VASELINE, weiß Ph.Eur., Salbe). The other arm will remain untreated (control). The application of the skin care product will be twice a day in the morning and in the evening for 4, respectively 8 weeks. This should be done after washing or showering to allow the product to stay on the skin during day/ night.

Subject instructions

The subjects should inform the Investigator before using any systemic treatment which may interfere with the study assessments. Some treatments are prohibited throughout the study.

During the study, the subjects will be instructed **not to**:

- have sun exposure or UV-light sessions on the investigational areas,
- Use any topical drug or cosmetic product on the investigational areas on both arms (except usual cleaning products) which may interfere with the trial assessment (topical hyaluronan, anti-inflammatory drugs, corticoids, retinoids, α-hydroxy acids, vitamin C).
- have physical treatments on the investigational areas.

3.3.1 Concomitant Treatments

Prohibited concomitant treatments

- Any topical drug (hyaluronan, anti-inflammatory drugs, corticoids, retinoids, vitamin C, corticoids, etc.) on investigational areas until the last assessment
- Any systemic treatment which may interfere with either investigational products or study conduct (anti-inflammatory drugs, corticoids, retinoids, vitamin C, corticoids, etc.) for more than 5 consecutive days until the last assessment
- Any treatment which may affect the blood coagulation and hemostasis (anticoagulant medications, NSAID, etc.)

Allowed concomitant treatments

The associated treatments which are considered necessary and not interfering with either investigational products or study conduct can be used on decision of the Investigator. The drug names (INN), their indication, dose and duration will be recorded in the CRF in concomitant treatments section.

3.4 Outcomes and variables

Because this is an exploratory study, no distinction is be made between primary and secondary outcomes.

Name	Method and metric	Time points of data collection		
Blistering Time	 Visual inspection Duration from start of suction pressure to appearance of first vesicles in minutes Duration from start of suction pressure to development of full blister in minutes (Appendix 4) 	Visit 3, Visit 5		
Skin surface Temperature	- Measurement with Skin- Thermometer ST 500 (Courage+Khazaka electronic GmbH) - Means of duplicate measurements per skin area in °C per skin area	Visit 3, Visit 5		
Stratum corneum hydratation (SCH)	- Corneometer CM 825 (Courage + Khazaka, Cologne, Germany) (Appendix 5) - Means of duplicate measurements per skin area in arbitrary units	Visit 1, Visit 2, Visit 3, Visit 4, Visit 5, Visit 6		
Epidermal and dermal hydratation	- Measurement with MoistureMeterEpiD (Delfin Technologies) (Appendix 6) - Percentage of tissue water (0- 100%) (0,5mm measurement depth)	Visit 1, Visit 2, Visit 3, Visit 4, Visit 5, Visit 6		
Epidermal thickness	- OCT (Thorlabs, Lübeck, Germany), measurements according to Trojahn et al. 2015 µm) (Appendix 8)	Visit 1, Visit 3, Visit 5, Visit 6		

Name	Method and metric	Time points of data collection
Age	Checking by looking at the ID card (metric)	Screening
Body temperature	Clinical thermometer in °C	Screening
Heart rate	Beats per minute (bpm)	Screening
Blood pressure	Millimeters of mercury (mmHg)	Screening
BMI (body height and weight)	kg/m ²	Screening
Phototype	Categories I, II, III	Screening

Both arms will be subdivided in two investigational areas, called "Area A" (upper part of the middle of the right volar forearm) respectively "Area C" (upper part of the middle of the left volar forearm) and "Area B" (lower part of the middle of the right volar forearm) respectively "Area D" (lower part of the middle of the left volar forearm) (Figure 1).

After 4 weeks (Visit 3) 2 suction blisters (Appendix 4) will be raised at the investigational Areas A or B at the right volar forearm (Figure 2). Another 2 suction blisters will be raised at the left volar forearm at the investigational Areas C or D (Figure 2). The allocation of the respective area for suction blister induction is decided via a randomization list.

After 4 additional weeks (Visit 5), 2 more suction blisters will be raised in each of the remaining so far non-blistered investigational Areas.

After the blister has been raised, the blister fluid will be punctured and a dressing applied to allow the wound to heal. The skin areas where suction blisters have been raised after 4 weeks will not be treated during the following 8 weeks.

Before any measurements or induction of the suction blisters, the study volunteers will be requested to acclimatize for 30 minutes at 40 to 60 % relative humidity and a temperature of 20 to 22 °C with having both forearms uncovered.

Sequence of measurements (Visit 1, 2, 3, 4, 5 and 6)

- (1) Skin surface temperature
- (2) Stratum corneum hydration (SCH)
- (3) Epidermal and dermal hydration
- (4) Skin thickness

Measurements will be performed two times per measurement area. Every value will be recorded separately.

Figure 1. Localization of investigational skin areas

[figure not shown]
[figure not shown]

Figure 2. Localization of suction blisters

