5.1 Data collection methods

All data collectors will be trained in obtaining accurately the variables of interest. Paper source data (SD) will be used to document all study variables of interest (data collection forms see appendix 3).

Medical examination

The medical examination performed before inclusion will include a subject's interview on her medical history and a clinical examination, to make sure of the subject's eligibility.

Suction blister creation

The Suction blister model is an artificial and controlled technique for dermal-epidermal separation. Over the course of this study a total of 8 suction blisters with 8 mm in diameter are produced at the middle of the volar forearms of one volunteer. The comparisons of the blistering times (in minutes) will be used as outcome to detect possible treatment effects. Two suction blisters will be induced on each investigational area for two independent measurements of the blistering time. The technical procedure of suction blister wound creation is presented in the SOP Appendix 4.

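### No single blistering-time contrast is named for the aim in section 2.2; four are equally eligible, which leaves room for selective emphasis in the conclusion

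*Combined protocol and SAP*

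**What the plan says.** Section 2.2 asks one directional question: "whether the use of a basic skin care formulation increases the mechanical integrity/adhesion of the dermo-epidermal junction". Section 5.1 names the variable that is to answer it: "The comparisons of the blistering times (in minutes) will be used as outcome to detect possible treatment effects".

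Section 3.4 gives the exploratory nature of the study as the reason that "no distinction is be made between primary and secondary outcomes". Blistering time then appears there with two metrics, both read by visual inspection: "Duration from start of suction pressure to appearance of first vesicles in minutes" and "Duration from start of suction pressure to development of full blister in minutes". Each is taken at two visits. The first set comes at four weeks ("After 4 weeks (Visit 3) 2 suction blisters" on each forearm) and the second at eight: "After 4 additional weeks (Visit 5), 2 more suction blisters will be raised in each of the remaining so far non-blistered investigational Areas".

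There are also replicates, under section 5.1: "Two suction blisters will be induced on each investigational area for two independent measurements of the blistering time". Section 3.4 says that duplicates are averaged for skin temperature and stratum corneum hydration, but it gives no combining rule for blistering time. Appendix 4, which covers blister creation and timing, is listed by title only in the text available, so a rule may be there.

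Section 5.3 describes each skin area at each visit by its median and interquartile range, shows the results in bar graphs, and rules out statistical tests. Section 3.6 plans 12 women without a formal calculation. Section 4.3 states that neither investigators nor participants are blinded.

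**The concern.** The plan has one question and one outcome for it, but does not say which form of that outcome carries the answer. If the four contrasts point the same way, little is lost. If they differ (for example, first vesicles later on the treated arm but full blisters not, or a difference at four weeks that is gone at eight), nothing written in advance says which result the conclusion should rest on. A reader of the report could not tell whether the highlighted contrast was always meant to lead or was picked because it looked best. An estimate can be selected in this way as easily as a p-value.

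The setting gives this some weight: 12 women, a visual endpoint, and assessors who know which arm was treated.

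Section 5.3 adds a second gap. Areas A and B are on the right forearm and C and D on the left (section 3.4), while the treated forearm is randomised (sections 3.3 and 4.1). A summary by anatomical area therefore does not line up with treated and control skin, and it does not use the within-woman pairing that the split-body design provides.

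**Working it through.** The plan states no power, alpha, effect size or SD, so there is no figure of its own to reproduce. The check is a count, followed by an illustration.

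**Count.** Definitions of blistering time (3.4): 2. Visits (3.4): 2. Contrasts of treated against untreated forearm: 2 × 2 = 4. This is a minimum, because the combining rule for the two blisters per area and the form of the contrast are also open in the text.

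**What 5.3 would produce.** Assume that each randomisation list in 4.1 allocates with probability 1/2. At Visit 3, Area A is then blistered in 12 × 1/2 = 6 women on average, and in 6 × 1/2 = 3 of them it is on the treated forearm. A literal summary for Area A would pool treated and untreated skin.

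**Illustration of free choice under no effect.** Inputs:
- n = 12 pairs (3.6).
- Median as the summary, as in 5.3, applied here to the paired treated-minus-control difference.
- Normal paired differences with mean 0 and SD 1 (assumed).
- Correlation r_d between the two definitions at a visit, r_v between the two visits for one definition, and r_d × r_v otherwise (all assumed; the documents give none).

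In each of 100,000 simulated trials, the four medians were computed and the largest was kept. The results are averages of that largest median, in SDs of the paired difference:

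| r_d | r_v | Mean of the largest of four medians |
|---|---|---|
| 0.80 | 0.50 | 0.257 |
| 0.90 | 0.50 | 0.237 |
| 0.95 | 0.80 | 0.180 |
| 0 | 0 | 0.356 (bound, not plausible) |

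A single contrast fixed in advance averaged 0.00 in every row.

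**Cross-check.** The expected maximum of four independent standard normals is 1.03. The last row implies a standard error of about 0.356 / 1.03 = 0.346 SD for one median of 12, against 1/√12 = 0.289 SD for a mean. A median is the noisier summary for normal data, so the direction is as expected.

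**Scale.** Against 0.346 SD, the shift is 0.180 / 0.346 = 0.52 to 0.257 / 0.346 = 0.74 of one standard error. It cannot be given in minutes because the plan states no SD. For every 10 minutes of SD in the paired difference it would be 0.18 × 10 = 1.8 to 0.257 × 10 = 2.6 minutes.

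**The case against.** The strongest reply is that the choice is declared and consistent. The title and sections 2.3, 3.4 and 3.6 all call the study exploratory, no test is planned and no power is claimed. Section 5.1 already singles out blistering time, so hydration, temperature and thickness are not serious rivals for answering 2.2. Section 5.3 commits to describing the blistering times for every area and visit, and 7.8 to a study report, registry results and a publication that follows CONSORT. Someone shown all of them could see any disagreement.

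Most of this stands, and it rules out three stronger readings that a reader might infer:

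- *That a type I error rate is inflated.* No alpha or test exists in the plan, so there is no error rate to breach.
- *That results will be hidden, or that the trial cannot answer its question without selection bias.* The plan is to describe everything. Bias arises only if someone selects, and what is open is the emphasis in the conclusion.
- *That the four contrasts are versions of one answer.* First vesicles and full blister are successive stages of the same blister, and four and eight weeks are different exposures. A pattern across them is a legitimate exploratory result. They are equally eligible under the plan, not equivalent.

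It is also fair that independence exaggerates the size. Two stages of one blister should be strongly correlated, so the 0.356 row is only a bound.

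What the reply does not meet is the gap itself. Being exploratory explains the absence of tests and of a sample size calculation. It does not require the main form of the one relevant outcome to be left unnamed. Reporting all four does not tell a reader which was meant to lead.

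**Conclusion.** The point holds as a moderate weakness that is cheap to repair. Four blistering-time contrasts are equally eligible to answer 2.2, none is preferred, and 5.3 does not define the treated-minus-control comparison that the aim needs. The consequence is a conclusion that cannot be shown to be free of selective emphasis.

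If the most favourable contrast were the one highlighted, its expected value with no true effect would be about 0.18 to 0.26 SD of the paired difference, instead of zero. That range rests on normal paired differences, medians of 12 pairs, and assumed correlations of 0.8 to 0.95 between definitions and 0.5 to 0.8 between visits. It describes full freedom of choice and is not a forecast of what the investigators will do. The count of four and the absence of a ranking come from the text alone and need no assumption.

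**What to change.** Make two linked edits before the first Visit 3, when blistering data first arise.

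1. **Section 3.4.** Name one blistering-time definition at one visit as the main outcome for 2.2. Time to full blister at Visit 5 is one example; the choice is the sponsor's. State how the two blisters per area are combined, consistently with Appendix 4.
2. **Section 5.3.** Summarise that outcome as the within-subject treated-minus-control difference, with its median and interquartile range. Label the other three blistering-time contrasts supportive and keep reporting all of them.

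Both sections have to change, because editing 3.4 alone would leave it at odds with a 5.3 that summarises by area. The registry entry, which section 1.2 places after ethics approval, should carry the same main outcome.

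The cost is a few sentences. The one downside is that the sponsor commits to a single headline contrast. No test, extra measurement or extra participant is needed, and the study remains exploratory.

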3.5 Participant timeline

Table 1. Participant timeline

	Visit 0 Screening	Visit 1 Inclusion	Visit 2	Visit 3	Visit 4	Visit 5	Visit 6
	D ₋₁₄ to D ₀	D_0	D _{14±1}	D _{28±2}	D _{42±2}	D _{56±2}	D _{66±3}
Informed consent	X						
Demography	X						
Medical history	X						
Vital signs	X						
Physical examination	X						
In-/exclusion criteria	X	X					
BMI	X						
Randomization of arms		Х					
Instruction how to treat the treatment arm		Х	Х	X	X		
Handout of products		Х		Х			
Treatment		4					
Record concomitant medication, therapies, procedures	X	Х	Х	X	Х	Х	Х
Investigational sites identification		Х					
Blister Induction*				Х		X	
Check for blister healing					Х		Х
Stratum corneum hydratation		X	Х	Х	Х	X	
Epidermal and dermal hydratation		Х	Х	Х	Х	X	
Epidermal thickness		Х		Х		X	
Record AEs		Х	Х	Х	Х	Х	Х
Return investigational products						X	

^{*}Randomization

3.6 Sample size

Due to the explorative character of this study, a formal sample size estimation is not performed. It is planned to include 12 healthy female subjects.

Subject replacement

In this study, a subject withdrawn from the study for any reason will be replaced.

3.7 Recruitment

Subjects will recruited via advertisements and/or contacted directly.

4 Methods: Assignment of interventions

There will be a concealed random allocation of the treatment arm (left vs. right) and area of suction blister induction ("Area A"/ "Area C" vs. "Area B"/ "Area D").

4.1 Allocation Sequence Generation

Two independent simple randomization lists (left vs. right arm and "Area A"/ "Area C" vs. "Area B"/ "Area D") will be created by the data manager not involved in the study. The data manager will also prepare sequentially numbered opaque sealed envelopes containing the allocation.

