5.3 Statistical methods

Demographic and other characteristics will be described using mean and spread parameters or proportions. The skin measurement results including the time(s) to blistering will be described using medians and interquartile ranges per skin area and time and displayed in grouped bar graphs. No statistical tests will be applied.

6 Methods: Monitoring

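### Minor: the treated forearm is drawn by simple randomisation for 12 subjects; a list of six right and six left would remove avoidable chance noise at almost no cost

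*Combined protocol and SAP*

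**What the plan says.** All references are to the combined protocol and SAP.

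- Section 4.1 generates the allocation from "Two independent simple randomization lists": one for the treated arm, one for the area blistered at Visit 3 (A and C, or B and D). No blocking or other restriction appears there or elsewhere.
- Section 3.6: "It is planned to include 12 healthy female subjects". It adds that "a subject withdrawn from the study for any reason will be replaced", without saying which side the replacement treats.
- Section 3.3: one forearm receives petrolatum and the other stays untreated, so within a subject treatment cannot be separated from side.
- Section 3.4: "Both arms will be subdivided in two investigational areas". A and B lie on the right forearm, C and D on the left. Blistering time is recorded only at Visits 3 and 5: "After 4 weeks (Visit 3) 2 suction blisters (Appendix 4) will be raised".
- Section 5.1: "The comparisons of the blistering times (in minutes) will be used as outcome to detect possible treatment effects".
- Section 5.3: skin measurements, including blistering time, are "described using medians and interquartile ranges per skin area and time". No tests are planned. Neither a within-subject difference nor a display by treated side is mentioned.

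**The concern.** Within one subject the treated-versus-control comparison is also a right-versus-left comparison. Only the mix of treated sides across subjects separates the two. With 12 subjects and an unrestricted list, that mix can be uneven. If right and left forearms blister at systematically different speeds, part of that difference then enters a summary that pools treated and control arms across sides. Blistering time has no pre-treatment value that could reveal or correct a side difference.

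What is at stake is some precision in the comparison that serves the aim in section 2.2. The validity of the randomisation is not in question. The second list does not contribute: both forearms of a subject are blistered at the same level at a given visit, so it leaves the treatment contrast at that visit untouched.

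**Working it through.** **No figure to reproduce.** The plan states no balance probability, power or sample size calculation.

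**Inputs.** Twelve subjects (section 3.6) and simple randomisation of side (section 4.1). Probability 1/2 per side is assumed, since no ratio is stated. The mean right-minus-left difference in blistering time, *s*, and the SD of within-subject arm differences, *d*, are not in the documents, so results are given for assumed ratios *s*/*d*.

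**Step 1, distribution of the split.** With *K* right-treated subjects, *K* ~ Binomial(12, 1/2) and P(*K* = *k*) = C(12, *k*)/4096.

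| Split | Calculation | Probability |
|---|---|---|
| 6:6 | 924/4096 | 22.6% |
| 7:5 | 2 × 792/4096 | 38.7% |
| 8:4 or worse | 2 × (495 + 220 + 66 + 12 + 1)/4096 = 1588/4096 | 38.8% |
| 9:3 or worse | 2 × (220 + 66 + 12 + 1)/4096 = 598/4096 | 14.6% |

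So 22.6% + 38.7% = 61.2% of allocations (2508/4096) are 7:5 or better.

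**Step 2, no bias.** In a pooled mean contrast the side difference contributes *s* × (2*K* − 12)/12. Since E(*K*) = 6, this averages zero over allocations. In one realised allocation it is *s*/6 at 7:5. This formula is for means and only shows the mechanism; section 5.3 plans medians.

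**Step 3, size for medians.** The difference between the treated-arm and control-arm medians was simulated under simple allocation and under a fixed 6:6 split. The setting was normal data, no treatment effect, an additive side difference, between-subject SD of *d* or 2*d*, and 200,000 studies per setting. The ratio of standard errors, simple to 6:6, was:

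- *s* = 0.25*d*: 1.005 to 1.015, a rise of about 1-2%.
- *s* = 0.5*d*: 1.031 to 1.056, a rise of about 3-6%.

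At *s* = 0 the two schemes are equivalent.

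**Step 4, adjusting in the analysis.** Averaging the right-treated and left-treated subgroup means cancels *s*, with variance (*d*²/4)(1/*k* + 1/(12 − *k*)) against *d*²/12 at 6:6. The standard error is larger than at 6:6 by a factor of 1.014 at 7:5, 1.061 at 8:4 and 1.155 at 9:3. The pooled mean has mean squared error *d*²/12 + [*s*(2*k* − 12)/12]². Setting the two equal gives break-even at *s* = 0.29*d*, 0.31*d* and 0.33*d*. Below about 0.3*d* the side average is the noisier estimate.

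**Step 5, predictability of a balanced list.** Once six of one side are used up, the remaining allocations are known. Their number is the length of the final run of the list. Averaged over all 924 orders it is 1584/924 = 1.7 allocations.

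**The case against.** The strongest reply is that this is a preference. Simple randomisation with numbered, opaque, sealed envelopes is valid, every subject is her own control, the study is exploratory without tests, and no section suggests that right and left forearms differ. If they do not, nothing is lost. Section 5.3 can also be read literally: results per skin area keep the sides apart, because each area belongs to one forearm. A balanced list, in turn, makes some allocations predictable.

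Most of this stands, and it sets the weight of the point. The literal reading does not settle the matter, though. Each area holds treated skin in some subjects and untreated skin in others, so a display strictly by area does not show the treatment comparison that section 5.1 relies on. How treated and control areas are brought together remains unstated.

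Three stronger readings are tempting, and the documents do not support them:

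- A reader might infer that the design fails whenever the split is not 6:6, that is in 77.4% of allocations. But 7:5 makes up half of those, and it is nearly harmless.
- A reader might infer a large loss of precision from calculations for a mean contrast or for a very large side difference. The plan uses medians, and no section supports a side difference as large as *d*.
- A reader might infer that a side-averaged estimate should be required. Step 4 shows that it costs precision when the side difference is small.

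**Conclusion.** The point holds as a cheap improvement of the lowest severity. An unrestricted side list for 12 subjects gives 8:4 or worse in 38.8% of allocations and 9:3 or worse in 14.6%. The consequence is chance noise in the treated-versus-control comparison of blistering time, and it would be wrong to call it bias.

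Any harm depends on two conditions that the documents leave open: a left-right difference shared across subjects, and pooling of treated and control arms without regard to side. If both hold, the loss for arm medians is about 1-2% in standard error at *s* = 0.25*d* and 3-6% at *s* = 0.5*d*. Those ratios are assumed, as are normal data, an additive side effect and probability 1/2 per side. The case for acting is that the change is nearly free, not that the loss is large.

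**What to change.** 1. **Section 4.1.** Replace the simple side list by one with six right and six left in random order. State that a replacement takes the withdrawn subject's side, held in a sealed duplicate envelope that is opened only after eligibility and consent, in line with section 4.2. Without this rule, replacement can undo the balance among completers. The blister-area list can stay as it is.
2. **Section 5.3.** Report the realised side split. Show treated-minus-control differences in blistering time by treated side at Visits 3 and 5, as description only, since each subgroup has about six subjects. Do not require a side-averaged estimate. If the list has already been made, this step can be taken alone.

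**Cost.** A different list from the data manager, duplicate envelopes, and one extra table or graph. No added subjects, visits or measurements.

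**Downside.** On average the last 1.7 allocations, and any inherited replacement side, become predictable to staff, who are unblinded under section 4.3. This is minor because every subject receives both conditions.
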